2.4 STATISTICAL METHODS

All the below statistical analyses are done for Cohort A and Cohort B separately. A pooled analysis is performed after all patients in the 2 cohorts have either finished the Month 7 visit during the fitusiran treatment period or discontinued from the study. Participants treated with fitusiran of 80mg QM and participants treated with fitusiran of 50mg Q2M will be analyzed separately. All the analysis will mainly focus on the participants treated with fitusiran of 80mg QM. The key efficacy, pharmacodynamic and safety data from participants treated with fitusiran of 50mg Q2M will mainly be listed due to the small sample size (only 2 participants). When safety analysis are mentioned in this doc, it refers to SAS1 and/or SAS 2 in this SAP.

2.4.1 Demographics and baseline characteristics

Continuous data are summarized using the number of patients (n), mean, standard deviation (SD), median, minimum, Q1, Q3, and maximum. Categorical and ordinal data are summarized using the number and percentage of patients.

Parameters are summarized by hemophilia type and overall on the EAS and Per-protocol analysis set. Analyses for the safety analysis set are included in the appendices if the size of the safety analysis set is different (>10%) from the size of EAS.

Medical and surgical history are summarized by system organ class (SOC) and preferred term (PT) sorted by internationally agreed order of SOC and by the decreasing frequency of PT within SOC.

No statistical testing on demographic and baseline characteristic data are performed.

No specific description of the safety parameters are provided at baseline. If relevant, the baseline values are described along with each safety analysis.

2.4.2 Prior or concomitant medications

The prior and concomitant medications are summarized by hemophilia type and overall for the safety analysis set.

Prior and concomitant medications are coded using the World Health Organization-Drug Dictionary (WHO-DD) currently in effect at Sanofi at the time of database lock. Results will be tabulated by anatomic therapeutic class (ATC) and preferred term.

Concomitant medications are tabulated by observation period (factor/BPA prophylaxis period and fitusiran prophylaxis period) and summarized separately for Factor/BPA prophylaxis medications, bleeding treatment medications and other concomitant medications. Any medications that did not end prior to first visit of the study are included. If an end date is missing or the medication is ongoing, the medication is included.

2.4.3 Study duration, extent of study treatment exposure and compliance

Fitusiran is the study treatment which is administrated by SC injection during the fitusiran treatment period for a total of 7 months.

Study duration, extent of study treatment exposure and compliance are assessed and summarized by hemophilia type and overall in the safety population.

Study duration in factor/BPA prophylaxis period in days is calculated as first dose date of fitusiran - enrollment date. Study duration in fitusiran treatment period in days is calculated as EOS/ET visit date - first dose date of fitusiran +1. Total study duration including AT follow-up in days is calculated as date of last follow up - enrollment date +1. The number of patients in each 2 months interval and summary statistics for the study duration are presented.

The extent of study treatment exposure is assessed by duration of treatment exposure in days and total number of fitusiran administrations received. Both of them will be summarized for fitusiran treatment period only.

For participants treated with fitusiran 80mg QM dose regimen, duration of treatment exposure in days is calculated as date of the last dose of fitusiran – the date of the first dose of fitusiran + 28. The number 28 is the number of days between two scheduled doses of fitusiran. For example, if the last dose of fitusiran is taken on day 31, the treatment exposure would be calculated as $(31-1) + 28 = 58$ days.

Dose interruptions and compliance are not taken into account for duration of exposure.

Fitusiran treatment compliance is calculated as the total mg dose received as the percentage of total mg dose expected to receive. Fitusiran treatment compliance is summarized.

2.4.4 Analyses of efficacy endpoints

Analyses for all the primary and secondary efficacy endpoints are conducted using EAS 1 as defined in Section 2.3. Listings of ABR will be provided for participants in EAS 2.

Baseline for fitusiran treatment period is defined as the last non-missing value on or before the date of first dose of fitusiran. Baseline for factor/BPA prophylaxis period is defined as the last non-missing value on or before the enrollment date (Month -6 visit date).

2.4.4.1 Analysis of primary efficacy endpoint(s)

2.4.4.1.1 Primary efficacy analysis based on on-treatment strategy

The primary objective of this study is to characterize the frequency of bleeding episodes while receiving fitusiran treatment, relative to the frequency of bleeding episodes while receiving factor/BPA prophylaxis. Including bleeding events in the period of intercurrent events such as use of prophylactic medication during fitusiran treatment period or surgery or after fitusiran treatment discontinuation could significantly bias fitusiran effect and make the comparisons difficult to interpret. The on-treatment strategy is considered of greatest relevance in assessing this primary objective (ICH E9 (R1), 2018 (1)).

Global protocol

The number of bleeding episodes is annualized for each patient using the following formula:

$$\text{Annualized bleeding rate (ABR)} = \frac{\text{total number of qualifying bleeding episodes}}{\text{total number of days in the respective period}} \times 365.25$$

The primary analysis includes all bleeding episodes occurring in the factor/BPA prophylaxis period and the fitusiran efficacy period.

Let λ_F represent the ABR during fitusiran efficacy period and λ_O represent the ABR during factor/BPA prophylaxis period. The null and alternative hypotheses of the primary analysis, respectively, can be written as follows:

$$H_0: \frac{\lambda_F}{\lambda_O} = 1 \quad H_A: \frac{\lambda_F}{\lambda_O} \neq 1$$

An estimated ABR ratio $\lambda_F/\lambda_O < 1$ and two-sided p-value < 0.05 from the significance test lead to the rejection of H_0 in favor of H_A ; it is concluded that prophylactic use of fitusiran reduces the frequency of bleeding episodes compared to the factor/BPA prophylaxis therapy.

The ABR ratio λ_F/λ_O is estimated using a repeated measures negative binomial model:

$$\log(\text{number of bleeding episode}) = \beta_0 + \beta_1 \cdot \text{study period} + \log(\text{duration})$$

$$\log(\text{number of bleeding episode}) = \beta_0 + \beta_1 \cdot \text{study period} + \log(\text{duration})$$

The number of bleeding episodes is the response variable. The study period (fitusiran treatment period or BPA prophylaxis period) is treated as a fixed effect and a robust sandwich covariance matrix is constructed to account for the within participant dependence. The logarithm of the duration (in years) that each patient spends in each study period matching the bleeding episode data being analyzed is included as an offset variable to account for unequal follow-up time due to early withdrawal, surgery, etc.

The ratio of ABR in the fitusiran treatment period to the BPA prophylaxis period, its 95% CI and p-value are presented. The p-value should be interpreted with caution. In addition, as a contrast Bayesian analyses are performed to summarize the point estimates of the posterior probability of a clinically significant treatment effect, along with associated measures of uncertainty. The estimated mean ABRs in these 2 periods along with their 95% CIs are presented from this model. In addition, median and interquartile range (Q1, Q3) for the observed ABR are summarized descriptively for each study periods.

Given that the primary analysis is based on on-treatment strategy, primary and secondary bleeding-related data during the efficacy and treatment periods are expected to be complete. No sensitivity analysis about the missing data mechanism is performed.

2.4.4.1.2 Efficacy analysis based on treatment policy strategy

A supportive efficacy analysis is performed by including all bleeding episodes collected through the end of the study, regardless of any premature treatment discontinuation, excluding only events due to major or minor surgeries based on EAS as in the primary analysis. The same repeated measures negative binomial model as in the primary analysis is used. It assesses the benefits of the fitusiran treatment policy strategy relative to factor/BPA prophylaxis treatment.

A sensitivity analysis to the above treatment policy analysis is performed by including all bleeding events (ie, not excluding bleeding events due to surgeries).

Missing data sensitivity analyses using controlled imputation

The above efficacy analysis assumes the uncollected bleeding events after study discontinuation are missing at random (MAR). Sensitivity analyses are performed to assess the robustness of this treatment policy analysis by imputing the missing data based on different missing data mechanism. The missing data is imputed using multiple imputation (MI) methods for recurrent event data based on pattern mixture models (Keene et al, 2014(2)) to assess the impact of different assumptions about the statistical behavior of post-withdrawal outcomes. The post-withdrawal part of each pattern-specific distribution is modelled using MAR and Copy Reference (CR) approaches. No missing data imputation is done for factor/BPA prophylaxis period since all the patients in EAS 1 complete factor/BPA prophylaxis period.

The MI is carried out in the following steps:

1. Fit a Bayesian negative binomial model with a noninformative prior to the observed data and obtain the posterior distributions of the event rate for both study periods.
2. Draw 100 independent samples from the conditional distribution of missing counts given the observed count and duration of each patient with missing data based on different post-withdrawal imputation models, described below, for fitusiran efficacy period (fitusiran treatment period for US protocol). The conditional distribution is also negative binomial.
3. The observed counts and imputed counts for each patient with missing data are summed.
4. Each 100 imputed datasets are then analyzed using the same repeated measure negative binomial regression model as in the primary analysis. Estimates from the model such as least square means and standard errors are then combined across imputation datasets using Rubin's formula, as implemented in the MIANALYZE procedure. These and their 95% confidence interval limits are then exponentiated to obtain the estimate of ABR for each study period and the estimate of the ABR ratio.

MAR and CR approaches are described below:

1. Missing at Random (MAR) Approach: Post-withdrawal missing bleeding events in fitusiran efficacy period (fitusiran treatment period for US protocol) are imputed using only the observed data during that period.
2. Copy Reference (CR) Approach: The expected ABR for a patient in the fitusiran efficacy period (fitusiran treatment period for US protocol) both pre- and post-withdrawal is assumed to be the same as that in the factor/BPA prophylaxis period. This accounts for a gradual loss of fitusiran effectiveness post-withdrawal. If a patient in fitusiran efficacy period (fitusiran treatment period for US protocol) has more events pre-withdrawal than expected if this patient had been in the factor/BPA prophylaxis period, then this "positive residual" feeds through into a higher than expected ABR in the post-withdrawal period. This is because this patient's earlier observed ABR higher than mean event rate suggests the patient has a higher propensity to have events.

The efficacy analysis based on treatment policy strategy may serve as sensitivity analyses for the primary efficacy analysis based on on-treatment strategy. It is important to note that the estimand based on on-treatment strategy (the primary efficacy analysis) is considered most relevant and applicable in characterizing the frequency of bleeding episodes while receiving fitusiran treatment, relative to bypassing agent (BPA) prophylaxis.

Per-protocol analysis

Efficacy analysis will be repeated on the per-protocol analysis set as defined in [Section 2.3](#).

Zero-inflated negative binomial model

To address the concern of potential excessive zero bleeding events, the above on-treatment and treatment policy efficacy analyses are repeated using the zero-inflated negative binomial model, and the results will be presented if model converges.

Bayesian analysis

A supportive efficacy analysis will be performed for the primary endpoint by using the Bayesian repeated measure Negative Binomial regression model. The informative prior distributions of the model parameters (eg, treatment effect, random effect, dispersion) may be used in the model. The ratio of ABR in the fitusiran efficacy period (fitusiran treatment period for US protocol) to the factor/BPA prophylaxis period, its 95% CI and the posterior probability of clinically significant treatment effect will be estimated. To assess sensitivity of the posterior distribution to this informative prior, an additional analysis will be performed using a neutral prior assuming mean ABR ratio of 1.

This Bayesian analysis will be implemented via PROC MCMC in SAS.

Covid-19 related sensitivity analysis

To address the impact of Covid-19, the above on-treatment and treatment policy efficacy analyses will be repeated on the Covid-19 unaffected set as defined in [Section 2.3](#). In addition, a sensitivity analysis based on on-treatment strategy will be performed by excluding the additional following intercurrent events:

- Period of missing at least two fitusiran doses in consecutive scheduled visits due to Covid-19 which is defined as one month after last dose (ie, last dose date + 29 days) before missing doses due to Covid-19 to one month after starting of re-dosing (ie, first re-dose date + 28 days). For participants treated with fitusiran 50mg Q2M dose regimen, replace the number of 28 with 56.
- Period from 6 months after enrollment of factor/BPA prophylaxis period to the date of first fitusiran dose if the date of first fitusiran dose was delayed due to Covid-19

The same negative binomial model as in the primary analysis will be used.

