1.3 DETERMINATION OF SAMPLE SIZE

Sample size is based on clinical considerations. The overall sample size of 80 patients including approximately 30 patients with inhibitor (Cohort A) and approximately 50 patients without inhibitor (Cohort B) was selected recognizing the limited number of patients with hemophilia, and to yield a reasonably robust estimate of the fitusiran bleeding episode rate and address the secondary objectives, including characterization of safety and tolerability. The proposed sample

size is also expected to provide reasonable precision around the ratio of bleeding rate in the fitusiran efficacy period to bleeding rate in the factor/BPA period for both Cohort A and Cohort B.

Since patients participate in multiple periods, within-patient correlation of numbers of bleeding episodes is expected between the periods. Having no prior knowledge of this correlation, different correlation scenarios were considered and the ratio of the bleeding rate in fitusiran efficacy period to the bleeding rate in factor/BPA period along with its 95% CIs were simulated. Below tables summarize the results from 10 000 simulated studies along with the ABR assumptions.

Table 1 - Simulated ratio of rates for Cohort A, with 95% confidence intervals

Correlation	Average Ratio (Average 95% CI Bounds), N=30 Based on 10 000 Simulations	
	Fitusiran period ABR: mean = 4, SD = 6	
	Factor/BPA period ABR: Mean = 16; SD = 14	Factor/BPA period ABR: Mean = 12; SD = 11
0.25	0.24 (0.14, 0.42)	0.32 (0.19, 0.57)
0.50	0.24 (0.15, 0.39)	0.32 (0.20, 0.52)
0.75	0.24 (0.17, 0.35)	0.32 (0.22, 0.47)

Abbreviation: ABR=annualized bleeding rate; BPA=bypassing agent; CI=confidence interval; SD=standard deviation
Note: Correlation = within-patient correlation between bleeding episodes of fitusiran efficacy period and factor or BPA period.

Table 2 - Simulated ratio of rates for Cohort B, with 95% confidence intervals

Correlation	Average Ratio (Average 95% CI Bounds), N=40 Based on 10 000 Simulations	
	Fitusiran period ABR: mean = 4, SD = 6	
	Factor/BPA period ABR: Mean = 4; SD = 5	Factor/BPA period ABR: Mean = 6; SD = 7
0.25	1.04 (0.57, 1.94)	0.69 (0.39, 1.25)
0.50	1.03 (0.63, 1.69)	0.68 (0.43, 1.09)
0.75	1.01 (0.72, 1.41)	0.67 (0.48, 0.93)

[figure not shown]
Abbreviation: ABR=annualized bleeding rate; BPA=bypassing agent; CI=confidence interval; SD=standard deviation

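### The controlled multiple imputation leaves out each patient's own complete prophylaxis-period bleed count, although the design is paired

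*SAP*

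**What the plan says.** SAP 2.4.4.1.2 adds missing-data sensitivity analyses to the supportive treatment-policy analysis.

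- Step 1 fits a Bayesian negative binomial model and takes a rate for each study period. No repeated-measures or patient-level term is named.
- Step 2: "Draw 100 independent samples from the conditional distribution of missing counts given the observed count and duration of each patient with missing data".
- MAR: "Post-withdrawal missing bleeding events in fitusiran efficacy period (fitusiran treatment period for US protocol) are imputed using only the observed data during that period".
- CR sets the mean to the prophylaxis-period rate both before and after withdrawal. It carries forward a residual when a patient "has more events pre-withdrawal than expected if this patient had been in the factor/BPA prophylaxis period". The SAP says this represents a gradual loss of effectiveness.
- Nothing is imputed for the prophylaxis period, "since all the patients in EAS 1 complete factor/BPA prophylaxis period".

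SAP 1.3 says that "within-patient correlation of numbers of bleeding episodes is expected between the periods" and simulates 0.25, 0.50 and 0.75. The Bayesian analysis of the primary endpoint, later in 2.4.4.1.2, is a repeated-measures negative binomial model run in PROC MCMC, and it lists a random effect among its example parameters.

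**The concern.** This is a switch study. The patient who leaves during fitusiran has already been followed for about six months on the reference regimen, with his bleeds counted. That count predicts his missing bleeds, and the imputation does not use it. MAR excludes it explicitly. For CR the omission is an inference from two places: step 2 conditions on one observed count and duration per patient, and the residual is framed hypothetically, as if the patient had been on prophylaxis, when he was.

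Two things follow. MAR draws are too low if heavier prophylaxis bleeders are the ones who leave, because an observed predictor of both is left out. CR reads a low count achieved on fitusiran as a low personal bleeding tendency, even where the prophylaxis record says otherwise. CR is the only departure from MAR planned for missing bleeds, since SAP 2.4.4.1.1 plans no missing-data sensitivity analysis for the primary estimand. A small gap between CR and MAR could then be taken as more reassurance than it is.

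**Working it through.** **Inputs (SAP 1.3 and 2.1.3.1).** "Fitusiran period ABR: mean = 4, SD = 6"; Cohort A "Factor/BPA period ABR: Mean = 16; SD = 14" or "Factor/BPA period ABR: Mean = 12; SD = 11"; Cohort B prophylaxis ABR 4 (SD 5) or 6 (SD 7). Efficacy period 162 days, so T = 162/365.25 = 0.4435 years; prophylaxis period 168 days, t0 = 0.4600. The documents give no withdrawal rate or time. I assume withdrawal after 81 of the 162 days, t1 = 0.2218, in 5, 10 or 20% of patients.

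**The plan's own figure first.** The SAP gives no figure for the imputation, so I checked the inputs against its Table 1 (Cohort A, prophylaxis ABR 16, N = 30). The variance of the log ratio is (CV1² + CV0² − 2ρ·CV1·CV0)/N, with CV1 = 6/4 = 1.5 and CV0 = 14/16 = 0.875. At ρ = 0.25 this is (2.25 + 0.766 − 0.656)/30 = 0.0786, SE 0.280, giving 0.25 (0.14, 0.43). The SAP states 0.24 (0.14, 0.42). At 0.50 and 0.75 I get 0.25 (0.16, 0.40) and 0.25 (0.17, 0.36), against 0.24 (0.15, 0.39) and 0.24 (0.17, 0.35). All agree within 0.01.

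**Dispersion.** k = (SD² − mean/T)/mean². For ABR 16: (196 − 36.1)/256 = 0.625. For fitusiran: (36 − 9.02)/16 = 1.686. I use both as a range.

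**Same fitusiran record, different history.** Prophylaxis mean 16, k = 0.625, one bleed in 81 days.

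- CR as written: 16 × (1 + 0.625 × 1)/(1 + 0.625 × 16 × 0.2218) = 8.1.
- MAR as written: 4 × (1 + 0.625)/(1 + 0.625 × 4 × 0.2218) = 4.2.
- The prophylaxis count y0 appears in neither formula. The results are the same for 2 prophylaxis bleeds (own ABR 2/0.4600 = 4.3) and for 20 (43.5).
- With y0 added under a frailty shared by both periods, CR is 16 × (1/k + y0 + 1)/(1/k + 16(t0 + t1)): 5.9 for 2 bleeds, 28.9 for 20.
- MAR becomes 4 × (1/k + y0 + 1)/(1/k + 16·t0 + 4·t1): 1.9 for 2 bleeds, 9.2 for 20.

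**Average patient leaving midway.** CR as written is m0(1 + k·4·t1)/(1 + k·m0·t1), where m0 is the prophylaxis ABR. With the own count at its expected value m0·t0, it is m0(1/k + m0·t0 + 4·t1)/(1/k + m0·t0 + m0·t1).

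| Prophylaxis ABR | CR as written | CR with own count |
|---|---|---|
| A, 16 | 5.7-7.7 (36-48%) | 12.3-12.6 (77-79%) |
| A, 12 | 5.5-6.9 (45-58%) | 9.6-9.8 (80-82%) |
| B, 6 | 4.6-4.9 (77-81%) | 5.4-5.5 (91%) |
| B, 4 | 4.0 (100%) | 4.0 (100%) |

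In Cohort A the own count closes 57-64% of the gap to the prophylaxis rate. For example, at ABR 16 and k = 0.625: (12.60 − 7.73)/(16 − 7.73) = 59%.

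**How strong is the shared-frailty assumption?** It implies a count correlation of k·a·b/√[(a + k·a²)(b + k·b²)], with expected counts a = 16 × 0.4600 = 7.36 and b = 4 × 0.4435 = 1.77. This is 0.66 at k = 0.625 and 0.83 at k = 1.686, that is, towards or beyond the top of the SAP's range. At lower correlation the own count adds less.

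**Effect on the ratio.** A fraction d leaving midway makes d/2 of fitusiran time imputed at rate x, so the ratio is [4 + (d/2)(x − 4)]/16. For Cohort A, ABR 16, k = 0.625:

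| Leaving midway (assumed) | MAR | CR as written | CR with own count | Full prophylaxis rate |
|---|---|---|---|---|
| 5% | 0.250 | 0.256 | 0.263 | 0.269 |
| 10% | 0.250 | 0.262 | 0.277 | 0.287 |
| 20% | 0.250 | 0.273 | 0.304 | 0.325 |

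For Cohort B at 6 vs 4 with 20% leaving and its own k = (49 − 13.5)/36 = 0.985, CR moves from 0.681 to 0.691. At 4 vs 4 it stays at 1.0.

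**The case against.** A reader might infer that CR fails because its imputed rate is below the prophylaxis rate, or that it shows only a fraction of the shift it was meant to show. The documents do not support that. The SAP describes CR as gradual loss, and an immediate return to the prophylaxis rate is a different assumption, jump-to-reference. Gradual loss also fits the plan's follow-up of antithrombin levels for up to six further months (Protocol 4.2). Part of the shortfall, 36-43% in Cohort A, remains after the own count is added and belongs to CR itself. One qualification: under the step 2 draw the imputed rate is constant after withdrawal, so the gradual loss appears as an intermediate level rather than a drift.

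Nor is the shortfall trial-wide. It is modest in Cohort B at 6 vs 4 and absent on average at 4 vs 4.

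The impact also depends on study withdrawal, not on stopping the drug. Patients who stop fitusiran are encouraged to stay and keep recording bleeds (Protocol 5.3.1 and 8.2.5.1; SAP 2.1.3.1), so little may be missing. And this is a sensitivity analysis of a supportive analysis; the SAP calls the on-treatment estimand the most relevant. All of this stands. It limits the size of the point, but gives no reason to leave out a complete, correlated count that is already in the database.

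**Conclusion.** The point holds in a limited form. The omission is explicit for MAR and follows from the wording for CR. Patients with very different prophylaxis records receive the same imputed rate, and MAR is biased low if heavier prophylaxis bleeders withdraw; whether they will is not known. The consequence for the Cohort A ratio is small: at prophylaxis ABR 16 and k = 0.625, using the own count raises the CR result by 0.007, 0.015 and 0.031 at 5, 10 and 20% withdrawal. None of these values comes near 1, so the planning figures do not suggest that the Cohort A conclusion is at risk.

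The figures rest on the planning means and SDs, on assumed mid-period withdrawal, and on one frailty shared across periods, which is the favourable case for the own count. This is a cheap improvement to a secondary stress test, not a flaw in the primary analysis.

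**What to change.** In SAP 2.4.4.1.2:

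1. Step 1: fit the Bayesian negative binomial model jointly to both periods with a patient random effect.
2. Step 2: draw missing counts conditional on the prophylaxis-period count and duration as well as the observed fitusiran-period count and duration.
3. MAR item: delete the clause that restricts imputation to data from the fitusiran period. CR item: reword the residual so that it uses the patient's actual prophylaxis record.
4. Keep CR as the gradual-loss scenario. If a full return to the prophylaxis rate is to be tested, add it as a separate, labelled jump-to-reference scenario based on the patient's own prophylaxis-period rate.

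Steps 3 and 4 of the SAP procedure are unchanged. The cost is SAP wording and some programming, in PROC MCMC, which is already planned; no new data are needed. Under the planning values the CR result in Cohort A would be slightly less favourable.
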